10.5.4 Abnormal Laboratory Values

Only clinically significant laboratory abnormalities that require active management will be recorded as AEs or SAEs on the CRF (e.g., discontinuation of study treatment, more frequent follow-up assessments, further diagnostic investigation, etc.).

If the clinically significant laboratory abnormality is a sign of a disease or syndrome (e.g., alkaline phosphatase and bilirubin 5 x the upper limit of normal associated with cholecystitis), only the diagnosis (e.g., cholecystitis) needs to be recorded on the Adverse Event CRF.

If the clinically significant laboratory abnormality is not a sign of a disease or syndrome, the abnormality itself should be recorded as an AE or SAE on the CRF. If the laboratory abnormality can be characterized by a precise clinical term, the clinical term should be recorded as the AE or SAE. For example, an elevated serum potassium level of 7 mEq/L should be recorded as “hyperkalemia”.

Observations of the same clinically significant laboratory abnormality from visit to visit should not be repeatedly recorded as AEs or SAEs on the CRF, unless their severity, seriousness, or etiology changes.

10.5.5 Preexisting Medical Conditions (Baseline Conditions)

A preexisting medical condition should be recorded as an AE or SAE only if the frequency, severity, or character of the condition worsens during the study. When recording such events on an Adverse Event CRF, it is important to convey the concept that the preexisting condition has changed by including applicable descriptors (e.g., “more frequent headaches”).

10.6 Grading and Relationship to Drug

The descriptions and grading scales found in the CTEP Version 4 of the NCI Common Terminology Criteria for Adverse Events (CTCAE) will be utilized for AE reporting. The location of the CTCAE CTEP V.4 is:

http://ctep.cancer.gov/protocolDevelopment/electronic_applications/ctc.htm

AEs not covered by specific terminology listed should be reported with common medical terminology and documented according to the grading scales provided in the CTCAE Version 4.

The relationship of event to study drug will be documented by the Investigator as follows:

- **Unrelated:** The event is clearly related to other factors such as the patient’s clinical state, other therapeutic interventions or concomitant drugs administered to the patient.
- **Unlikely:** The event is doubtfully related to the investigational agent. The event was most likely related to other factors such as the patient’s clinical state, other therapeutic interventions, or concomitant drugs.
- **Possible:** The event follows a reasonable temporal sequence from the time of drug administration, but could have been produced by other factors such as the patient’s clinical state, other therapeutic interventions or concomitant drugs.
- **Probable:** The event follows a reasonable temporal sequence from the time of drug administration, and follows a known response pattern to the study drug. The event cannot be reasonably explained by other factors such as the patient’s clinical state, therapeutic interventions or concomitant drugs.
- **Definite:** The event follows a reasonable temporal sequence from the time of drug administration, follows a known response pattern to the study drug, cannot be reasonably explained by other factors such as the patient’s condition, therapeutic interventions or concomitant drugs; AND occurs immediately following study drug administration, improves upon stopping the drug, or reappears on re-exposure.

10.7 Reporting Adverse Events

Table 2. Guidelines for Routine Adverse Event Reporting for Pilot Studies (Regardless of Expectedness)

Attribution	Grade 1	Grade 2	Grade 3	Grade 4
Unrelated			X	X
Unlikely			X	X
Possible	X	X	X	X
Probable	X	X	X	X
Definite	X	X	X	X

All routine AEs occurring between the start of intervention until 30 days after the last intervention or until the event has resolved, the study patient is lost to follow-up, the start of a new treatment, or until the study investigator assesses the event(s) as stable or reversible, will be reported. New information will be reported when it is received.

10.8 Serious Adverse Events

10.8.1 Definition

A serious adverse event (SAE) is any adverse event (experience) that in the opinion of either the investigator or sponsor results in **ANY** of the following:

- Death
- A life-threatening adverse event (experience). Any AE that places a patient or patient, in the view of the Investigator or sponsor, at immediate risk of death from the reaction as it occurred. It does NOT include an AE that, had it occurred in a more severe form, might have caused death.
- Inpatient hospitalization or prolongation of existing hospitalization (for > 24 hours). Admission for scheduled nephrectomy will not be considered an SAE.
- A persistent or significant incapacity or substantial disruption of the ability to conduct normal life functions
- A congenital anomaly or birth defect
- Important Medical Event (IME) that, based upon medical judgment, may jeopardize the patient and may require medical or surgical intervention to prevent one of the outcomes listed above

10.8.2 Reporting Serious Adverse Events

All new SAEs occurring from the date the patient signs the study consent until 30 days after the last intervention or a new treatment is started, whichever comes first, will be reported. The RPCI SAE Source Form is to be completed with all available information, including a brief narrative describing the SAE and any other relevant information.

SAE's occurring after the 30 day follow-up period that the investigator determines to be possibly, probably or definitely related to the study intervention, should be reported.

SAE's identified as an Unanticipated Problem by the Investigator must be reported. Please refer to **Section 10.9.2** for details on reporting Unanticipated Problems.

10.8.3 Investigator Reporting: Notifying the AGS-003 manufacturer

SAEs that meet requirements for expedited reporting (probably or definitely related to AGS-003) and are inconsistent with the safety profile in the current AGS-003 IB must be rapidly reported to Argos.

Argos Therapeutics, Inc.
[name]
Ph. [contact]
[contact]

10.8.4 Follow-Up for Serious Adverse Events

All related SAEs should be followed to their resolution, the study patient is lost to follow-up, the start of a new treatment, or until the study investigator assesses the event(s) as stable or irreversible. New information will be reported when it is received.

10.9 Unanticipated Problems

10.9.1 Definition

An Unanticipated Problem (UP) is any incident, experience, or outcome that meets all of the following criteria:

- Unexpected (in terms of nature, severity, or frequency) given:
 - The research procedures that are described in the study-related documents, including study deviations, as well as issues related to compromise of patient privacy or confidentiality of data.
 - The characteristics of the patient population being studied.
- Related or possibly related to participation in the research (possibly related means there is a reasonable possibility that the incident, experience, or outcome may have been caused by the procedures involved in the research).
- Suggests that the research places patients or others at a greater risk of harm (including physical, psychological, economic, or social harm) than was previously known or recognized and if in relation to an AE is also deemed serious per Section 10.8.

10.9.2 Reporting Unanticipated Problems

Unanticipated problem reporting will begin at the time of participant consent. The Unanticipated Problem Form will be submitted to CRS Compliance Office within 1 business day of becoming aware of the Unanticipated Problem. After review, CRS Compliance will submit the UP to the IRB.

When becoming aware of new information about the Unanticipated Problem, submit this updated information to CRS Compliance with an updated Unanticipated Problem Form. The site Investigator or designated research personnel will report all unanticipated problems, whether related or unrelated to the investigational agent(s) to the **IRB in accordance with their local institutional guidelines**.

10.10 FDA Reporting

When RPCI is the IND holder the following describes the FDA reporting requirements by timeline for AEs and new safety findings that meet the criteria outlined below:

Within 7 Calendar Days

Any adverse event that meets ALL the following criteria:

- Related or possibly related to the use of the study drug;
- Unexpected; and
- Fatal or life-threatening.

Within 15 Calendar Days

Any adverse event that meets ALL the following criteria:

- Related or possibly related to the use of the study drug;
- Unexpected; and
- Serious but not fatal or life-threatening.

Or, meets ANY of the following criteria:

- A previous adverse event that is not initially deemed reportable but is later found to fit the criteria for reporting (report within 15 days from when event was deemed reportable).
- Any findings from other studies, including epidemiological studies, pooled analysis of multiple studies, or other clinical studies conducted with the study drug that suggest a significant risk in humans exposed to the drug.
- Any findings from animal or in vitro testing that suggest a significant risk for human patients including reports of mutagenicity, teratogenicity, or carcinogenicity or reports of significant organ toxicity at or near the expected human exposure.
- Any clinically important increase in the rate of occurrence of a serious, related or possibly related adverse event over that listed in the protocol or investigator brochure.

Sponsors are also required to identify in IND safety reports, all previous reports concerning similar adverse events and to analyze the significance of the current event in the light of the previous reports.

Reporting Process

The principal investigator or designee will complete and submit a FDA Form 3500A MedWatch for any event that meets the above criteria. Forms will be submitted to the CRS Compliance Office via email to [contact].

10.11 Gene Therapy Study Reporting of Serious Adverse Events

Studies that involve Gene Therapy will report SAEs as described above and will be reported to the Office of Biotechnology Activities (OBA) / NIH.

Any SAE that is fatal or life-threatening, that is unexpected, and associated with the use of the gene transfer product must be reported to the FDA and NIH OBA as soon as possible, but not later than 7 calendar days after the Sponsor's initial receipt of the information.

SAEs that are unexpected and associated with the use of the gene transfer product, but are not fatal or life-threatening, must be reported to the FDA and NIH OBA as soon as possible, but not later than 15 calendar days after the sponsor's initial receipt of the information.

If, after further evaluation, an adverse event initially considered not to be associated with the use of the gene transfer product is subsequently determined to be associated, then the event must be reported to the NIH OBA within 15 days of the determination.

Any follow-up information relevant to a SAE must be reported within 15 calendar days of the Sponsor's receipt of the information. If a SAE occurs after the end of a clinical trial and is determined to be associated with the use of the gene transfer product, that event shall be reported to the NIH OBA within 15 calendar days of the determination.

The Principal Investigator or delegated research staff will submit a report to the CRS Compliance Office via email: CRS Compliance for all gene therapy SAEs. The Compliance office will forward the information to ORSP.

Completed reports may be sent via U.S. mail, courier service, e-mail, or facsimile to:

NIH Office of Biotechnology Activities
[name]
[name]
(For all non-USPS deliveries use Zip Code 20817)
[contact]
[contact]
E-mail address for Reporting Adverse Events: [contact]
General E-mail: [contact]
Website: <http://oba.od.nih.gov/oba/index.html>

Additional information for reporting adverse events, including a report template, can be found at: http://oba.od.nih.gov/rdna/adverse_event_oba.html.

11 DATA AND SAFETY MONITORING

The RPCI Data and Safety Monitoring Board will assess the progress of the study, the safety data, and critical efficacy endpoints. The DSMB will review the study annually and will make recommendations that include but not limited to; (a) continuation of the study, (b) modifications to the design (c) or termination of the study.

12 STATISTICAL METHODOLOGY

The primary objective of this study is to assess immune-modulatory systemic and intratumoral effects of AGS-003 as neoadjuvant treatment in patients with localized renal cell carcinoma.

The time component will be modeled as a three-level classification factor. The full model for the effects of time will be fit using Linear Mixed Model methods. The model will include a random patient effect and 5 fixed effects for time and the interactions. The presence of any time effect will be assessed with full-reduced model Type 3 test. If the omnibus test is statistically

significant at the $p < 0.05$ level, then three pairwise time-point comparisons will be conducted. Expression measurements may be transformed to satisfy modeling assumptions. This methodology accommodates patients with incomplete follow-up information.

Patient, disease and treatment characteristics will be summarized using common descriptive statistics and graphical aids. P values less than 0.05 will be deemed statistically significant. No adjustments will be made to control the overall Type I error rate.

12.1 Sample Size Determination

A maximum of 10 patients will be enrolled in this study. In previous experiments, immune marker expression measurements varied widely, with means between 8.0 and 1,200; the coefficient of variation has been between 0.5 and 1.0 depending on the marker, method of measurement and disease setting. For power calculations, the possible effect of immunotherapy delivery model of expression has been ignored, and the (original scale) expressions are assumed to have mean (standard deviation) of 100 (75), and within-patient correlation = 0.50. If the measurements are log-normally distributed, the log-transformed outcome would have mean (standard deviation) of about 4.38 (0.68).

Comparing measurements at two time points, the within-patient effect of immunotherapy on an immune marker can be assessed using a permutation paired t-test. A paired t-test with a two-sided significance threshold of 0.05 has 80% power to detect a mean of at least 5.08 in the post-measurements, if the pre-measurements are as described above: a 20% increase in the mean on the original scale.

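### Section 12.1 calls a log-scale shift of 0.70 a 20% increase. It is about a doubling, and power for a true 20% increase is about 12%, not 80%.

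*Combined protocol and SAP*

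**What the plan says.** Section 12.1 (Sample Size Determination) sets the size of the trial: "A maximum of 10 patients will be enrolled in this study". For the power calculation it takes an original-scale "mean (standard deviation) of 100 (75), and within-patient correlation = 0.50". If the measurements are log-normal, it converts these to a log-scale mean of about 4.38 with SD 0.68. It notes that the coefficient of variation (CV) has ranged from 0.5 to 1.0 across markers, methods and disease settings.

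For two time points, it says the within-patient effect "can be assessed using a permutation paired t-test". It then claims, at a two-sided 0.05 threshold, "80% power to detect a mean of at least 5.08 in the post-measurements", and ends the sentence by describing that effect as "a 20% increase in the mean on the original scale". No other section corrects or qualifies the 20%.

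**The concern.** The closing phrase translates a difference between two log means into a percentage change, and the translation does not follow from the numbers beside it. A log-mean difference of 0.70 is a ratio of about 2, not 1.2. One sentence therefore attaches 80% power to two effects that differ about five-fold in size.

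This is the plan's only power statement for the immune endpoint, which is the primary objective. Someone relying on the 20% could read a null marker result as evidence against a modest change, although the design would miss a true 20% increase about 88% of the time. The Rationale (Section 2) says that the expected immune responses would lead to a larger Phase II study. A designer who carried forward 20% with 10 patients would under-size that study badly.

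**Working it through.** **Inputs, all from Section 12.1:** n = 10 pairs; original-scale mean 100 and SD 75 (CV 0.75); within-patient correlation 0.50; log mean 4.38 and log SD 0.68; detectable post-treatment log mean 5.08; two-sided alpha 0.05; CV range 0.5 to 1.0.

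**Step 1. The log-scale inputs.**
- Log variance = ln(1 + 0.75²) = ln(1.5625) = 0.446, so log SD = 0.668 (plan: 0.68).
- Log mean = ln(100) − 0.446/2 = 4.382 (plan: 4.38).

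Both agree with the plan apart from slight rounding of the SD.

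**Step 2. The plan's power figure.**
- SD of paired differences = 0.68 × √(2 × (1 − 0.50)) = 0.68.
- Shift = 5.08 − 4.38 = 0.70.
- Noncentrality = (0.70/0.68) × √10 = 3.26, with 9 degrees of freedom.
- Power = 82.5% by the paired t-test, and 81.8% by the permutation version (200,000 simulated trials, all sign flips).
- The shift with exactly 80% power is 0.677 (post-treatment log mean 5.06). Nine pairs give 77.2% at a shift of 0.70, so 10 is the smallest number that reaches 80%.

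The statement about a log mean of 5.08 is therefore sound.

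**Step 3. Back-transform the shift.**
- With the same log SD before and after, the ratio of original-scale means is exp(0.70) = 2.01.
- With log SD 0.68, the means are exp(4.38 + 0.68²/2) = 100.6 and exp(5.08 + 0.68²/2) = 202.6, an increase of about 101%.
- At exactly 80% power, the ratio is exp(0.677) = 1.97, an increase of 97%.

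**Step 4. Power for a true 20% increase.**
- Shift = ln(1.2) = 0.182, so the post-treatment log mean is about 4.56.
- Noncentrality = (0.182/0.68) × √10 = 0.85.
- Power = 11.8% (SD 0.68), 12.1% (SD 0.668) or 11.7% (permutation test).
- Pairs needed for 80% power: 112 (SD 0.68) or 108 (SD 0.668).

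**Step 5. The plan's CV range** (n = 10, correlation 0.50, unrounded log SD):

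| CV | Log SD | Shift with 80% power | Detectable increase | Power for +20% |
|---|---|---|---|---|
| 0.5 | 0.472 | 0.470 | 60% | 19% |
| 0.75 | 0.668 | 0.665 | 95% | 12% |
| 1.0 | 0.833 | 0.829 | 129% | 10% |

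**Step 6. Other readings that might recover 20%.**
- Ratio of the log means: 5.08/4.38 = 1.16. This is neither 1.20 nor a change on the original scale.
- Original-scale SD held at 75 after treatment: a log mean of 5.08 then corresponds to a mean of about 175, or +75%.
- Paired t-test on the original scale: shift 20, SD of differences 75, power 11.8%.
- Correlation of 0.50 placed on the original scale: log-scale correlation = ln(1 + 0.50 × 0.5625)/0.446 = 0.555 and SD of differences 0.630. The detectable ratio is 1.87, and power for 20% is 13.0%.
- Correlation needed for 80% power at 20% with 10 pairs: about 0.96, against the assumed 0.50.

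None of these gives 20%.

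**The case against.** The strongest reply is that the power calculation itself did not fail. The effect it specifies is a post-treatment log mean of 5.08, and 10 pairs give slightly more than 80% power for it. That is correct: the error lies in the translation to 20%, and the 12% belongs to that translation. But the sentence presents the two as the same effect, and the percentage is the part most readers will remember.

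A second point also stands. The 12% describes one marker compared at two time points with 10 complete pairs. Section 12 plans a linear mixed model over three time points, with an omnibus test before any pairwise comparison, so 12% is not the power of that analysis and should be labelled accordingly. Any missing pair would lower it.

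Third, the trial is a pilot with a cap of 10. The plan does not say that 10 was derived from the power target, Section 12.4 separately gives operating characteristics of the stopping rule at 10, and no decision rule uses the 20%. Misreading of a null result is therefore a risk rather than a documented consequence. This supports leaving the sample size alone. It does not support leaving a wrong detectable effect in the only power statement for the immune endpoint.

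**Conclusion.** The concern holds. The stated 20% is wrong by about a factor of five: under the plan's own assumptions, the effect detectable with 80% power is roughly a doubling (+97% at exactly 80% power, +101% at the stated log mean of 5.08). Power for a true 20% increase is about 12%. The 80% claim for a log mean of 5.08 is right and can stay.

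This rests on log-normal measurements, equal log SD before and after treatment as the paired t-test set-up implies, correlation 0.50 and 10 evaluable pairs. Moving the correlation to the original scale, using the unrounded SD, or varying the CV from 0.5 to 1.0 leaves power for a 20% increase between about 10% and 19%.

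**What to change.** Replace the end of the power sentence in Section 12.1 with wording such as:

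> For a single marker compared at two time points in 10 evaluable patients, the paired t-test has 80% power to detect a log-scale post-treatment mean of about 5.06, that is, roughly a doubling (about a 97% increase) of the mean on the original scale, assuming the same log-scale SD before and after treatment. Power for a 20% increase is about 12%. For coefficients of variation from 0.5 to 1.0, the detectable increase ranges from 60% to 129%.

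Keeping 5.08 is equally acceptable if the text says at least 80% power and about a 100% increase. Correcting the 20% is the essential part; the 12% figure and the CV range keep the limits of the pilot visible to whoever plans the next study.

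The cost is a rewrite of one sentence and a less favourable stated sensitivity. No patients, procedures or analyses are added, and the sample size stays at 10.

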12.2 Efficacy Analysis

The efficacy analysis discussed above will be conducted using all patients with at least two time point measurements.

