4 METHODOLOGY

4.1 Study Design

This is a non-randomized, single center Pilot study treating patients with non-metastatic RCC with the autologous dendritic cell AGS-003 as a neoadjuvant treatment prior to extirpative radical or partial nephrectomy.

Eligible patients will be administered the AGS-003 as a single, fixed dose of 1.2×10^7 DCs, delivered as an intradermal injection (0.6 mL per dose delivered as three separate 0.2 mL injections per full dose) once weekly for a total of 3 doses beginning at Injection Week #1, followed by a partial or radical nephrectomy at the Nephrectomy Visit. Blood will be taken for immunological analysis at the time of the first dose, after the 3rd dose, and at End of Study.

All patients will sign an informed consent prior to study related tests. All patients will meet the inclusion and exclusion criteria. Patients will be treated on an outpatient basis. Kidney surgery will require inpatient admission postoperatively.

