6.5 Treatment Discontinuation

All patients who discontinue due to an AE must be followed until the event resolves or stabilizes. Appropriate medical care should be provided until signs and symptoms have abated, stabilized, or until abnormal laboratory findings have returned to acceptable or pre-study limits. The final status of the AE will be reported in the patient's medical records and the appropriate eCRF.

Reasons for treatment discontinuation should be classified as follows:

- Death
- Progressive disease
- Treatment-related toxicity
- Toxicity unrelated to treatment
- Investigator judgment

- The Investigator may withdraw a patient if, in his/her judgment, it is in the patient's best interest to do so
- Noncompliance
- Patient voluntary withdrawal
- A patient may withdraw from the study at any time, for any reason. If a patient discontinues treatment, an attempt should be made to obtain information regarding the reason for withdrawal.
- Sponsor decision
- Development of active autoimmune disease or other condition requiring chronic immunosuppressive therapy (such as rheumatoid arthritis, systemic lupus erythematosus, multiple sclerosis, organ transplant recipient, etc.)
- If, while on study, a patient shows any evidence of tumor progression independent of any SAE, study treatment will be discontinued, the patient's RCC will be restaged, and the study investigator will discuss possible treatment options (including definitive therapy) with the patient.
- If the study product is delayed > 2 weeks, the patient will discontinue the study and be allowed to proceed directly onto surgery and, the patient would be replaced in the study.

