8.5 End of Study Visit/ Follow-Up

The end of study visit is conducted approximately one month following nephrectomy, or any time the subject discontinues the study. The following assessments will be performed:

- Physical examination including vital signs and weight
- Hematology: Complete Blood Count with automated differential (CBC/DIFF)
- Chemistry: Complete Metabolic Panel (P22 COMP)
- Blood draw for Immunological analysis
- Blood draw for Autoimmunity assessment
- Pregnancy test (urine) in females of childbearing potential
- ECOG Performance Status (see **Appendix A**)
- Concomitant medication
- Adverse events (surgical AEs only if clinically significant)

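### Section 12.2 leaves patients with a single immune measurement out of a mixed model that could use them; keeping treated patients with one value is a small, free improvement.

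*Combined protocol and SAP*

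**What the plan says.** Section 4.1 plans three immune blood draws: "Blood will be taken for immunological analysis at the time of the first dose, after the 3rd dose, and at End of Study". Section 12 treats these as the time factor: "The time component will be modeled as a three-level classification factor". It states the model as "The model will include a random patient effect and 5 fixed effects for time and the interactions" (what the five effects are is a separate question). It then says of the approach: "This methodology accommodates patients with incomplete follow-up information".

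Section 12.2 defines the analysis set in one sentence: the analysis will be "conducted using all patients with at least two time point measurements". Patients with two of the three values stay in, and patients with one are left out. The plan gives no reason for the threshold, no expected rate of missing samples and no missing-data assumption.

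Three other provisions affect how many patients could have one value. The Nephrectomy Visit (Section 8.4.4) and the End of Study visit (Section 8.5) each include an immune draw. The End of Study visit is held about a month after surgery, "or any time the subject discontinues the study". A patient whose product is delayed by more than two weeks leaves the study, and "the patient would be replaced in the study" (Section 6.5).

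**The concern.** A likelihood-based mixed model does not need two values per patient. A patient with only a pre-dose value still informs the baseline mean and, through the within-patient correlation, the estimated change. Leaving that patient out has two consequences.

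The first is a small loss of precision, in a trial where "A maximum of 10 patients will be enrolled in this study".

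The second is a change in what is estimated: the mean change among patients who were re-measured. With a correlation below 1, the expected change depends on the baseline value. If patients with unusually low or high baselines were more likely to lack later samples, those who remain would tend to regress toward the mean. With no concurrent control arm, that drift could be read as an effect of AGS-003. Under missing at random, keeping the lone baselines in the model corrects for this.

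**Working it through.** **Inputs from Section 12.1.** N = 10; log-scale mean 4.38 and SD s = 0.68; within-patient correlation ρ = 0.50; two-sided 0.05; 80% power for a post-treatment mean of 5.08. **Assumptions, because the documents give no figure:** the number m of patients with a baseline value only (1 to 3), the loss mechanism, and the chance q that a sample fails (10% to 20%).

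**The plan's own figure.** The SD of the paired difference is 0.68 × √(2 × (1 − 0.50)) = 0.68, and the change is 5.08 − 4.38 = 0.70. The exact paired t-test reaches 80% power at N = 10 and not at N = 9 (82.5% and 77.2%). The sample size is therefore reproduced, with power slightly above the stated 80%.

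**Precision.** Let n = 10 − m patients have both values.
- Two-value rule: variance = 2s²(1 − ρ)/n.
- All patients kept (ρ taken as known): variance = s²[(1 − ρ²)/n + (1 − ρ)²/(n + m)].

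With s² = 0.4624 and ρ = 0.50 these become 0.4624/n and 0.4624 × (0.75/n + 0.025).

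| m | n | SE, two-value rule | SE, all kept | Variance ratio |
|---|---|---|---|---|
| 1 | 9 | 0.227 | 0.224 | 0.975 |
| 2 | 8 | 0.240 | 0.234 | 0.950 |
| 3 | 7 | 0.257 | 0.247 | 0.925 |

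For ρ between 0.7 and 0.3 (assumed range) the reduction runs from 1.5% (m = 1, ρ = 0.7) to 10.5% (m = 3, ρ = 0.3).

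**Bias, worst case.** For a patient whose standardised baseline is z, the expected change is δ − (1 − ρ)·s·z, where δ is the true change. Suppose the m lowest of 10 baselines are exactly the ones lost. The expected values of the three largest of 10 standard normal values are 1.539, 1.001 and 0.656, and the lowest mirror them. The mean z among those kept is then the sum of the first m of these divided by 10 − m. Multiply by (1 − ρ)·s = 0.34:
- m = 1: 1.539/9 = 0.171, bias −0.058
- m = 2: 2.540/8 = 0.318, bias −0.108
- m = 3: 3.196/7 = 0.457, bias −0.155

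Losing the highest baselines gives the same sizes with a positive sign. Relative to the standard errors above these are 0.26, 0.45 and 0.60. In simulation with no true effect, the paired t-test rejects about 6.0%, 7.4% and 9.0% of the time instead of 5%.

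**Bias, softer cases.** If the chance of loss rises gradually with baseline (logistic, about 2 of 10 lost), the simulated bias is 0.065. If 2 of 10 are lost completely at random, it is zero within simulation error. A random-intercept REML fit to all patients at ρ = 0.50 has bias within 0.007 of zero in every one of these simulated cases, including loss of the highest 1 or 2 baselines.

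**How many patients.** If each of the three samples fails independently with probability q, the expected number with baseline only is 10·q²·(1 − q): 0.09 at q = 0.1 and 0.32 at q = 0.2, per marker. Counting a lone value at any of the three times triples this, to 0.27 and 0.96.

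**The case against.** The strongest reply is that the protocol already limits the problem. A baseline-only patient must miss both later draws, yet a patient who stops early is still scheduled for the End of Study draw at discontinuation. A patient removed because RNA isolation or amplification failed leaves before the first immune draw and has no pre-dose value to lose. This stands, and it is why the expected number is well below one per marker.

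A second reply is that two values are a natural requirement for studying within-patient change, and that the permutation paired t-test in Section 12.1 needs them. That explains how the threshold may have arisen. However, Section 12.1 is the power calculation. The analysis set out for the primary objective in Section 12 is the mixed model, which has no such requirement.

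Some stronger conclusions are tempting but not supported:
- A reader might infer that Section 12.2 contradicts Section 12. It does not: patients with two of three values are still analysed, so the statement about incomplete follow-up remains true.
- A reader might infer that the change estimate will be biased. No passage links loss of samples to baseline immune status. The worst-case figures assume that exactly the most extreme baselines are lost.
- A reader might combine the 0.27 to 0.96 patients per marker with those bias figures. The two do not belong together: independent sample failure is loss completely at random and causes no bias.

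**Conclusion.** The point holds as a free improvement, not as a flaw that threatens the trial's conclusions. The two-value rule gives up 2.5% to 7.5% of the variance of the pre/post change if 1 to 3 of 10 patients have a baseline value only (ρ = 0.50). It also leaves the estimate open to a regression-to-the-mean bias of at most about 0.06 to 0.16 log units for the same numbers lost. That is below one standard error, and it is zero if loss is completely at random.

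These figures rest on the SD and correlation in Section 12.1 and on assumed numbers and mechanisms of loss. The likely number of affected patients is small.

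A reader might also infer that keeping every value removes any bias. That is so only under missing at random and with a covariance structure that fits. If, for example, correlation decays with time while the model assumes it is constant, some bias can remain.

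**What to change.** In Section 12.2, replace the restriction with a sentence to this effect: the linear mixed model includes all patients who received AGS-003 and have at least one immune measurement; the analysis restricted to patients with two or more time points is reported as a sensitivity analysis. Add that the primary analysis assumes missing at random, and name the covariance structure.

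The condition of having received AGS-003 matters. A patient who leaves before the first dose could still give a sample at the discontinuation visit, and that value would enter the End of Study level of the time factor without any exposure.

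The cost is one or two sentences, with no new data, visits or patients. A short table of how many patients have one, two or three values for each marker would show whether the choice made any difference.
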